The goal of this proof-of-concept study is to investigate the effect of ketamine on the symptoms of OCD in adolescents and young adults ages 14-22. The symptoms of OCD are evaluated using a number of validated scales designed to measure their clinical status. The specific aims of the study are as follows:

Aim 1. To assess the acceptability, feasibility and tolerability of a single ketamine infusion in adolescents and young adults with OCD.

Aim 2. To assess the effects of ketamine on OCD severity.

Primary Hypothesis:

Adolescent and young adult OCD patients will have a reduction in OCD symptoms immediately following the ketamine infusion.

Description of Subject Population

Sample #1

Specify subject population Individuals with obsessive-compulsive disorder Number of completers required to accomplish study aims 10 Projected number of subjects who will be enrolled to obtain required number of completers 20

Age range of subject population 14-22 inclusive

Gender, Racial and Ethnic Breakdown

Based on our experience and the demographics of the catchment area served by our institution, we expect the subject racial distribution to be approximately 73% White, 18% Black, 9% Asian, and for the ethnic distribution to be approximately 22% Hispanic. We expect the sample to be 50% female. Description of subject population

We will recruit 10 adolescents and young adults (post-pubertal, ages 14-22) with OCD using similar criteria as in the prior study in adults ¹⁴ with the modification that participants have had at least one adequate trial of an SRI medication and a course of CBT for OCD. They will be free of medication or on a stable dose of an SRI medication, score \geq 16 on the Children's Yale-Brown Obsessive Compulsive Scale (CYBOCS) prior to entering the study and report at least moderate severity of obsessions and/or compulsions.

Recruitment Procedures

Describe settings where recruitment will occur The study will recruit participants from the Anxiety Disorders Clinic (ADC), directed by [name], as

well as the CAPES Evaluation Service and the Children's Day Unit (CDU), which are directed by [name]. The ADC screens over 200 adults (\geq 18) with OCD a year. The CAPES/CDU provides free expert consultation, evaluation, and treatment referrals for children and adolescents suffering from mood and anxiety disorders. OCD self-help organizations such as the International OCD Foundation will be contacted to further publicize the existence of this study.

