In order to be eligible for this study, participants must be off all psychotropic medications aside from SRIs and other types of drugs likely to interact with glutamate for at least 14 days prior to starting the study. After consent is signed, if a medication washout is necessary, it can either be performed by a psychiatrist at the Pediatric Anxiety & Mood Research Clinic (PAMRC) or by the participant's own physician. During this washout period, patients will be monitored at least weekly in person and by phone more frequently if needed. Weekly assessments during the washout period will include the Clinical Global Impressions Scale (CGI-S). If a patient's score on the Global Improvement section of the CGI is a 6 ("much worse") or 7 ("very much worse") during the washout period, the clinician will take the patient off the protocol washout and initiate the 3-month open clinical treatment offered to all patients at the end of the study. Patients may independently elect to withdraw from standardized treatment at any time for any reason, independent of their CGI Global Improvement score. Physical exam, vital signs and adverse events will also be carefully assessed during the washout period.

Day 1: Baseline Evaluation & Ketamine Infusion

Baseline Evaluation

After completing the screening procedures and medication washout if applicable, participants will proceed to the baseline evaluation. Baseline evaluation procedures include:

- *Efficacy Assessments:* Children's Yale-Brown Obsessive Compulsive Scale (CYBOCS), Children's Depression Rating Scale-Revised (CDRS-R), Young Mania Rating Scale (YMRS), Clinician Administered Dissociative States Scale (CADSS), Brief Psychiatric Rating Scale (BPRS), OCD Visual Analogue Scale (OCD-VAS), Yale-Brown Obsessive Compulsive Challenge Scale (YBOCCS), Child Obsessive-Compulsive Impact Scale-Revised (COIS-R)
- *Feasibility and Safety Assessment*: Columbia-Suicide Severity Rating Scale (C-SSRS)
- Clinical Global Impressions Scale (CGI)
- Medical Assessment: Vital Signs and Pregnancy Test (urine) for female participants

Test Day Procedures

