It is planned that the ketamine infusion take place on an inpatient unit at the Irving Institute for Clinical & Translation Research at CUMC. After completing the baseline evaluation, if a participant is eligible for the study, they will be escorted to the Irving Institute by PAMRC staff. For the infusion, the participant's treatment team will comprise of a nurse, a Pediatric Advanced Life Support (PALS) certified pediatrician [name] and the study MD ([name]). At the site of the infusion, a nurse will repeat the participant's vital signs, place the IV, and set up the IV infusion pump. The ketamine infusion can begin as soon as PALS-certified pediatrician is present. After the infusion, the study MD and PALS certified pediatrician will remain present to monitor the participant throughout the 2-hour post-infusion observation period.

Ketamine Infusion

Each participant will receive one slow intravenous infusion of 0.5mg/kg ketamine hydrocholoride. The infusion will be given over a course of 40 minutes. The study PI will meet with the research pharmacist and technician responsible for the preparation of infusions several days prior to the subject's first test day. EKG will constantly be monitored prior to, during, and after the ketamine infusion. Blood pressure, heart rate and oxygen saturation will be monitored and recorded at 5-minute intervals at baseline and throughout the ketamine infusion.

In addition to these medical assessments, after 20 minutes from the start of the infusion, the study MD will monitor participants closely using the Clinician Administered Dissociative States Scale (CADSS) and Clinical Global Impressions Scale (CGI). Participants will also be asked to complete the 1-item OCD Visual Analogue Scale (OCD-VAS) to monitor OCD symptoms over a rapid time frame.

Safety and Termination of Ketamine Infusion

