Yale-Brown Obsessive Compulsive Scale, Child version (CYBOCS): The CYBOCS is a semi-structured measure of OCD severity with excellent inter-rater reliability, internal consistency, and test-retest reliability. It is validated in those starting at age 7 and used in studies up to age 20. The CYBOCS differs from the adult YBOCS only in its use of simpler language. The CYBOCS will be administered by IE at screening and 120 minutes post-infusion to determine OCD severity. The CYBOCS will also be administered by IE at baseline, day 7, and day 14 and will be the primary outcome measure. As secondary outcomes, response will be defined as a CYBOCS decrease of \geq 30% and excellent response as a CYBOCS of \leq 10 following the Pediatric OCD Treatment Study (2004). The CYBOCS checklist will be used to determine symptom dimensions.

Children's Depression Rating Scale-Revised (CDRS-R): The CDRS-R is a 17-item clinician-administered semi-structured interview with good inter-rater reliability and validity that assesses 17 symptom areas related to depression, including those that serve as criteria in the DSM-IV. It provides an overall index of severity of depression. This assessment will be administered by IE at screening and 120 minutes post-infusion and by IE at baseline, day 7 and day 14.

Clinical Global Impressions Scale (CGI): This is a clinician rated instrument providing a single score for severity and improvement (from a 7-point scale) comparing the patient's condition during each visit on treatment to the condition at baseline (before treatment). The CGI will be administered by both IE and the study MD as per the study flow chart.

Columbia-Suicide Severity Rating Scale (C-SSRS): This is a semi-structured clinician rating of suicidal behavior, suicide attempts, and presence and intensity of suicidal ideation. The assessment will be administered by study MDs at screening, baseline, day 3 or 4, day 7, and day 14.

Young Mania Rating Scale (YMRS): YMRS is an 11- item clinician administered scale for rating manic symptoms. It will be administered by the study MD at baseline, 120 minutes post-infusion, day 3 or 4, day 7, and day 14.

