6 OUTCOMES

6.1. Primary Outcomes

Primary outcomes will be the changes in the CY-BOCS total score and CGI-S rating from baseline to 14 days post infusion.

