6.2. Secondary Outcomes

Secondary outcomes will be the changes in the OCD-VAS and Y-BOCCS total score from baseline to 14 days post infusion.

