7 STATISTICAL ANALYSIS

Data will be analyzed using IBM SPSS. We will report descriptive statistics and results from paired sample-tests to describe changes in primary and secondary outcomes from baseline to 14 days post infusion. The following subsections describe the statistical procedures.

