8.2. Statistical Tests

In the initial SAP, we proposed a mixed-effects regression to analyze the potential efficacy of the ketamine infusion. After study completion and careful consideration of the data collected, we decided to change the SAP to compare the mean differences of the primary and secondary outcomes between the baseline assessment and 14 days post infusion using paired sample t-tests.

The normal distribution of the differences between the paired values will be tested using the Shapiro-Wilk test and outliers will be reviewed using box plot diagrams. Estimated t-values, 95% confidence intervals, and p-values will be presented for each outcome variable.

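### The protocol's primary hypothesis is an effect immediately after the infusion, but the revised SAP tests all four efficacy outcomes only at day 14

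*Protocol*

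**What the plan says.** **Hypothesis.** Under Specific Aims and Hypotheses, the protocol's primary hypothesis is: "Adolescent and young adult OCD patients will have a reduction in OCD symptoms immediately following the ketamine infusion". Aim 2, in both protocol and SAP, is to assess the effect of ketamine on OCD severity and gives no timing.

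**Protocol outcome.** The Assessment Instruments section says of the main scale: "The CYBOCS will also be administered by IE at baseline, day 7, and day 14 and will be the primary outcome measure". The same entry also lists a CYBOCS at 120 minutes post-infusion.

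**Revised SAP outcomes.** Section 6.1: "Primary outcomes will be the changes in the CY-BOCS total score and CGI-S rating from baseline to 14 days post infusion". Section 6.2: "Secondary outcomes will be the changes in the OCD-VAS and Y-BOCCS total score from baseline to 14 days post infusion".

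**Revised SAP analysis.** Section 7 promises "results from paired sample-tests to describe changes in primary and secondary outcomes from baseline to 14 days post infusion". Section 8.1 limits the descriptive statistics to the same primary and secondary outcomes. Section 8.2 specifies paired t-tests of baseline against day 14 and records when this was decided: "After study completion and careful consideration of the data collected, we decided to change the SAP to compare the mean differences".

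**Infusion-day data.** The protocol's Ketamine Infusion section says: "Participants will also be asked to complete the 1-item OCD Visual Analogue Scale (OCD-VAS) to monitor OCD symptoms over a rapid time frame". Its Post-Infusion section has OCD-VAS and CGI recorded as soon as the infusion ends. Section 3 of the revised SAP also describes OCD-VAS ratings before, during and after the infusion, but no later section assigns them an analysis.

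**The concern.** A hypothesis about the minutes or hours after an infusion cannot be tested by a contrast two weeks later unless the effect is assumed to persist, and the protocol does not assume that. Direct Benefits to Subjects separates the immediate remission reported in adults from the improvement that some of them kept for up to a week. The section on minimizing risks expects relief to be temporary for some participants.

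A day-14 result therefore bears on durability. No change at day 14 is compatible with a large immediate effect that wore off. A reduction at day 14 does not show when it began. The ratings that do bear on the hypothesis have no planned summary or test.

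This matters because promising data are meant to support a grant application for a full-scale randomized trial. Without a clear statement, readers could take the day-14 p-values as the answer to the protocol's primary hypothesis.

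**Working it through.** The documents give no power, effect-size or SD figure on this point, so there is none to reproduce. The check sets the hypothesis beside each planned contrast and each scheduled rating.

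**Step 1: planned contrasts in the revised SAP.** Sections 6.1 and 6.2 give 2 + 2 = 4 outcomes. Sections 7 and 8.2 test each once, baseline against day 14.

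| Time point | Planned contrasts |
|---|---|
| Infusion day, any time | 0 of 4 |
| Day 7 | 0 of 4 |
| Day 14 | 4 of 4 |

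**Step 2: ratings scheduled on the infusion day.** All four instruments are in the Day 1 Baseline Evaluation list, so each has a pre-infusion value. For later ratings that day:

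| SAP outcome | Infusion-day rating in the protocol | How firmly the text fixes it |
|---|---|---|
| OCD-VAS | During the infusion and immediately after it | In the procedures text and in SAP section 3. The 20-minute time is attached to CADSS and CGI; the OCD-VAS sentence follows without a time of its own |
| CGI-S | CGI at 20 minutes and immediately after | In the procedures text, but as CGI; whether the severity item was scored is not stated |
| CY-BOCS | 120 minutes post-infusion | In the instrument list only; the infusion-day procedures do not repeat it |
| Y-BOCCS | During and after the infusion | Times are left to the study flowchart, which was not among the documents available |

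All 4 of 4 instruments have an infusion-day rating named in the protocol. Two have it in the procedures text, one in the instrument list only, and one through the flowchart only. OCD-VAS alone is fixed by the text in exactly the form the SAP analyses.

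**Step 3: can *immediately* be read as day 14?** The Post-Infusion section uses the word literally, for ratings taken when the infusion ends. The longest duration the protocol cites for the adult effect is one week, and 14 / 7 = 2, so the only test falls at twice that duration.

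**Step 4: did the initial SAP cover it?** Its outcome list gives CY-BOCS at baseline, week 1 and week 2. Its section 8.2 mentions the baseline-to-post-infusion difference in obsessional severity, but as a fixed effect in the model. That is a predictor, so it was not a clear pre-specified test of the hypothesis either.

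**Step 5: what infusion-day estimates could show.** The half-width of a 95% CI for a mean paired change, in SDs of the change, is t(0.975, n − 1) / √n:

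- n = 5 (SAP): 2.776 / 2.236 = 1.24 SD
- n = 10 (protocol): 2.262 / 3.162 = 0.72 SD

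These intervals are wide, so any infusion-day result is an estimate for description.

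**The case against.** The strongest reply is that the conflict starts in the protocol. It places its main measure of change under the Day 2–14 heading and names CYBOCS at baseline, day 7 and day 14 as primary. The revised SAP keeps that instrument and one of those times. The hypothesis may be loosely worded, with *immediately* meaning rapid compared with the 2–3 month lag of SRIs. Part of this stands: the fault is shared between the documents. The loose reading does not, because the protocol uses the word literally and separates immediate from maintained effect.

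Second, the count of four instruments overstates what is secure. That is fair: three of the four depend on the flowchart or on what was actually collected, so the remedy is conditional for them. The gap does not depend on them, because OCD-VAS alone would allow an infusion-day summary. A rating taken during the infusion is also only indirect evidence about what follows it.

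Third, a day-14 reduction is weak, indirect evidence of an earlier effect. That is granted, but it is still not a test of an immediate one.

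Fourth, this is a pilot whose Aim 1 is acceptability, feasibility and tolerability, and adding contrasts now is another change made after the data were seen. Both points are true. They favour descriptive reporting of every time point, but they do not excuse silence: the revised SAP still reports t-values, confidence intervals and p-values, and was itself settled after the data were considered.

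**Conclusion.** The concern holds. None of the 4 planned efficacy contrasts in the revised SAP addresses the protocol's primary hypothesis, although the protocol names an infusion-day rating for all 4 instruments. The day-14 tests do serve Aim 2; the conflict is with the hypothesis.

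A secondary gap is day 7. All four instruments are scheduled then, and day 7 is one of the protocol's CYBOCS primary-outcome times, yet 0 of 4 contrasts use it.

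The conclusion rests on reading *immediately* as the protocol uses it elsewhere, and on the text alone for the rating schedule. If the flowchart or the collected data lack the Y-BOCCS, the 120-minute CYBOCS or an acute CGI-S, fewer instruments can be reported, but the gap remains. This should be fixed before results are reported.

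**What to change.** In revised SAP sections 6.1, 6.2, 7, 8.1 and 8.2:

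1. Keep the day-14 outcomes and state that they do not address the protocol's hypothesis of an immediate reduction.
2. Add the estimate, n and 95% CI for change from pre-infusion to every infusion-day time point collected: OCD-VAS, Y-BOCCS, CGI-S if the severity item was scored, and CYBOCS at 120 minutes if collected. Show all of them; do not single out one instrument or time now that the data have been seen.
3. As a secondary item, report day-7 changes in CYBOCS, OCD-VAS, Y-BOCCS and CGI-S in the same form.
4. Label every added contrast as specified after data collection. Week-1 CY-BOCS may be noted as a listed outcome of the initial SAP. The post-infusion obsessional-severity term there should not be presented as pre-specification.

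The minimum acceptable change is item 1 plus a table of infusion-day n, mean and SD.

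The cost is SAP wording and a few estimates from data already scheduled, after checking the flowchart for the Y-BOCCS times and the 120-minute CYBOCS. The downside is that the acute ratings are uncontrolled and open-label, partly self-reported while drug effects are present, few in number, and added after the data were seen. They should be read as description and not as confirmatory tests.

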Have there been any study findings, recent literature, or untoward events occuring here or at other sites in the past year which might affect the analysis of the safety, risks or benefits of study participation? No

Have there been any serious adverse events (serious and/or unanticipated problems involving risks to subjects or others at this site which occured in the past year)?

No

Have all study staff with a significant role in the design or implementation of the human subject components of this study received required training in human research subject protections?

Yes

Is the study covered by a certificate of confidentiality?

No

Approved sample size 10 Total number of participants enrolled to date 5 Number of participants who have completed the study to date 4 Have there been any significant deviations from the anticipated study recruitment, retention or completion estimates? No Comments / additional information

Sample Demographics

Specify population Adolescents and young adults with OCD Total number of participants enrolled from this population to date 5 Gender, Racial and Ethnic Breakdown

We have screened a total of 9 participants and completed the study with 4 participants. 1 participant is currently in the 3-month follow-up period.

Gender:

- Male:1

- Female: 4

Race/Ethnicity:

- White: 4

- Mixed race: 1

Summary of Current Year's Enrollment and Drop-out

Number of participants who signed consent in the past year 3 Number of participants currently enrolled 1 Did the investigator withdraw participants from the study? No Did participants decide to discontinue study involvement? No

Procedures

To create the protocol summary form, first indicate if this research will include any of the following procedures

- ✓ Psychiatric Assessment
- Collection of Biological Specimens
- ✓ Medication Trial
- ✓ Medication-Free Period or Treatment Washout
- ✓ Off-label Use of Drug or Device

Population

Indicate which of the following populations will be included in this research

- ✓ Children (ages 13-17)
- Adults

Research Support/Funding

Will an existing internal account be used to support the project? Yes Describe internal account

PC002246 YAC Columbia account

903-4081A RFMH account

903-4132A RFMH account

Is the project externally funded or is external funding planned? Yes Select the number of external sources of funding that will be applicable to this study

Funding Source #1

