Is the PI of the grant/contract the same as the PI of the IRB protocol? Yes Select one of the following The grant/contract is currently funded Source of Funding Other Sponsor

NYPH YAC (Youth Anxiety Center) Select one of the following Single Site Business Office CU Does the grant/contract involve a subcontract? No

Study Location

Indicate if the research is/will be conducted at any of the following **NYSPI**

Other Columbia University Medical Center Facilities

This protocol describes research conducted by the PI at other facilities/locations No

Lay Summary of Proposed Research

Lay Summary of Proposed Research

This pilot study is proposed to determine the acceptability, feasibility and potential efficacy of ketamine, a medication that modulates glutamate in the brain, as a rapid treatment for obsessive-compulsive disorder (OCD) symptoms in adolescents and young adults with OCD. This study will recruit 10 youth (ages 14-22) who are diagnosed with clinically significant OCD and have failed at least one adequate trial of a Serotonin Reuptake Inhibitor (SRI) medication and a course of Cognitive-Behavioral Therapy (CBT) for OCD in the past. Participants will receive a single infusion of intravenous ketamine and be assessed at regular intervals post-infusion for up to 14 days. At the end of the 14-day treatment phase, all participants will be offered three months of open treatment for OCD with medication and/or CBT. The study will be conducted at NYSPI and will follow similar methodology to the approved protocol that studied the effects of ketamine in adults with OCD (IRB#5833, PI: [name], now being analyzed under IRB#7219, PI: [name] [name]). Promising data will lead to a grant application to the National Institutes of Mental Health for a full-scale randomized controlled trial.

Background, Significance and Rationale

Background, Significance and Rationale

Overview:

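### The stated sample sizes (20 enrolled, 10 completers, 10 approved and recruited, 5 in the SAP) do not reconcile, and the protocol does not say whom each one counts

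*Protocol*

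**What the plan says.** The sizes appear in these places:

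- **Protocol, Description of Subject Population, Sample #1.** "Number of completers required to accomplish study aims 10", followed directly by "Projected number of subjects who will be enrolled to obtain required number of completers 20".
- **Same section, description of the population.** "We will recruit 10 adolescents and young adults (post-pubertal, ages 14-22) with OCD".
- **Protocol, Lay Summary.** Also 10 to be recruited.
- **Protocol, enrolment report before Sample Demographics.** "Approved sample size 10 Total number of participants enrolled to date 5", then "Number of participants who have completed the study to date 4". Sample Demographics adds that 9 people were screened and that 1 is in the 3-month follow-up. For the past year the report records no withdrawals by investigator or participant. It answers No to significant deviations from the recruitment, retention or completion estimates.
- **SAP, section 3 (Procedures), initial and revised versions.** Both plan to recruit 5, with an age range of 14-20 where the protocol has 14-22. Section 8.2 of the revised version says that its change of method was decided after study completion, yet section 3 still says 5.

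Under Study Procedures, Screening, consent comes before the screening assessments, so a count of people consented includes screen failures. Neither document gives a drop-out rate, a power calculation or a precision target.

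**The concern.** The protocol ties 10 completers directly to accomplishing its aims, and a reader will take that as the size on which the conclusions rest. The same section says that 20 must be enrolled to get there, while the approved and recruited number is 10. If these numbers count the same people, the approved size cannot reach the projected enrolment. If they count different people, the labels *enrolled*, *recruit* and *approved sample size* need definitions, and none is given.

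Two things are at stake. The first is precision: the interval for a mean change depends heavily on whether there are 5, 8 or 10 pairs. The second is the feasibility result. Aim 1 concerns acceptability and feasibility, and the initial SAP makes the numbers screened and completing its primary outcomes, reported as totals and percentages. A percentage needs a named denominator. Without one, the protocol's answer that completion has not deviated from its estimates cannot be checked, because the estimate could be 10 of 20 or 10 of 10.

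**Working it through.** **Inputs.** Required completers 10, projected enrolment 20, approved and recruited 10, screened 9, enrolled 5, completed 4, in follow-up 1 (all protocol); recruited 5 (SAP, both versions).

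**1. The plan's own figure.** Required enrolment = completers / completion rate. The figure of 20 is reproduced at a rate of 0.5: 10 / 0.5 = 20. This is circular, because the 50% is itself obtained as 10 / 20.

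**2. The approved 10 read as a cap on enrolment.** Expected completers = 10 × rate; the chance that all 10 complete = rate^10.

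| Completion rate | Source | Expected completers of 10 | Chance that all 10 complete |
|---|---|---|---|
| 0.50 | implied by 10/20 | 5 | 0.001 |
| 0.80 | 4 of 5 so far | 8 | 0.107 |
| 0.90 | illustration | 9 | 0.349 |
| 1.00 | 5 of 5 if the follow-up case counts | 10 | 1 |

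**3. How much the accrual says.** 4 + 1 = 5, so every enrolled participant is accounted for. Completion is 4/5 (exact 95% CI 28% to 99%), or 4/4 among those with a final status. These counts favour 8 to 10 completers but cannot exclude 50%: the chance of 4 out of 4 at a true rate of 0.5 is 0.5^4 = 0.0625.

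**4. The 20 read as people consented.** The screened-to-enrolled yield is 5/9 = 56%. To enrol 10 at that yield takes 10 / (5/9) = 18 screened, close to 20. The numbers therefore fit a plan of about 20 consented and 10 treated. This still requires *enrolled* to mean consented in the population section, whereas the enrolment report uses it for 5 people out of 9 screened.

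**5. The SAP's 5.** At most 5 of 5 can complete, which is below 10 at any completion rate.

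**6. Precision.** The revised SAP uses paired t-tests with 95% confidence intervals from baseline to day 14. Half-width in units of the SD of the paired differences = t(0.975, n−1) / √n:

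- n = 5: 2.776 / 2.236 = 1.24 SD
- n = 8: 2.365 / 2.828 = 0.84 SD
- n = 10: 2.262 / 3.162 = 0.72 SD

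Relative to 10 pairs, the interval is about 1.2 times as wide at 8 (0.84 / 0.72) and 1.7 times at 5 (1.24 / 0.72).

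**7. Denominators.** The same 4 completers are 4/5 = 80% of those enrolled or 4/9 = 44% of those screened.

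**The case against.** The strongest defence is that nothing conflicts: 20 counts everyone who consents, 10 counts those treated, and consent precedes screening. Step 4 shows that the numbers fit. The accrual report also shows no loss after enrolment so far, and its No on deviations agrees with its own counts. In a proof-of-concept pilot with no stated power basis, the sizes may be seen as administrative entries. Actual counts will in any case replace the projections, since the revised SAP was written after study completion.

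Much of this stands. It rules out three stronger inferences that a reader might draw:

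- **That the trial yields about 5 completers by its own figures.** This needs two unwritten assumptions: that the 10 and the 20 count the same people, and that half are lost after enrolment. The only observed completion data point to 8 to 10.
- **That 10 × 5/9 = 5.6 confirms it.** The 5/9 is a screened-to-enrolled yield, so the result would count people enrolled, not completers. It also treats the approved 10 as a cap on people screened, although the report sets that 10 beside an enrolled count that excludes screen failures.
- **That a shortfall is established.** The documents do not report the final number of completers.

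The defence does not remove the inconsistency. The protocol never says that 20 means consented, and its one accrual report uses *enrolled* in the other sense. The defence also does not reach the SAP's 5, which both versions give as a recruitment plan and not as a count of participants obtained.

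**Conclusion.** The point holds as a failure of the stated sizes to reconcile, not as a forecast of low yield. The figures of 20, 10 and 5 cannot all be right under a single meaning of *enrolled*, and no meaning is given.

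If the approved 10 caps enrolment, 10 completers allows no loss at all. The expected number is then 5 to 10: 5 if the implied 50% applies after enrolment, 8 to 10 if the reported accrual continues. If 20 counts people consented and 10 counts people treated, the protocol's numbers can coexist, but the wording must say so. On either reading the SAP's recruitment of 5 contradicts the requirement for 10 completers. Between 10 and 5 completers, the confidence half-width for a paired change runs from 0.72 to 1.24 SD.

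The discrepancy itself is certain. The yield is conditional and rests on very few participants. The SD-unit half-widths assume the revised SAP's paired analysis and need no assumed effect size or SD.

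**What to change.** No extra patients are needed.

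1. Define *enrolled* once, as consented or as infused, and use it in the enrolment report, the lay summary and the population section. State what the approved 10 counts.
2. Define *completed* as well. The accrual report does not count the participant in the 3-month follow-up as complete, whereas the Follow-up Treatment section speaks of completing the 14-day period.
3. Correct the projected 20, the recruited and approved 10, and the SAP's 5 so that they agree. If the 5 is carried over from a different plan, say so and replace it.
4. State expected completers as a range with its assumption (5 to 10 if 10 caps enrolment), and beside it the half-widths of about 1.24, 0.84 and 0.72 SD at 5, 8 and 10 pairs.
5. In the results, report the actual numbers screened, infused and completing against the required 10, and name the denominator of each feasibility percentage.

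The cost is a wording change in the protocol form, a corrected number and a sentence or two in the SAP, and a participant-flow line in the report. The stated precision may look less favourable than 10 completers suggests.
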